6.3.3 Screening

Trained RAs will be responsible for screening potentially eligible participants from the FHCs and FGPs. Once a potentially eligible patient is identified for this study, they will be screened by telephone using a standardized form that outlines the study's inclusion and exclusion criteria. Study staff will obtain verbal consent prior to beginning the eligibility screening. Only participants that meet all eligibility criteria will be scheduled for a subsequent face-to-face meeting to obtain written informed consent.

6.3.4 Recruitment, Enrollment and Retention

Providers will be recruited through in-service talks at the clinics. Four methods, described below, will be employed to recruit the maximum number of eligible patient participants. Signed informed consent will be obtained from participants who meet the study eligibility criteria.

Method 1: Recruiting Using EHRs through EPIC: We will use EPIC to identify potentially eligible patients seen in the FHC/FGPs, based on DRG codes indicating presence of type 2 diabetes. We will develop a roster of potentially eligible patients for each treating physician in the practice. Physicians will be asked to review the roster and indicate, for each patient, whether an intervention targeting tracking patient-reported outcomes via text messaging is appropriate. Lists of patients deemed appropriate (i.e., "yes") by the physician will be generated. Following permission from FHC/FGP treating physicians to recruit their patients to the study, patients will be approached and screened using the following process: (a) A letter signed by the treating physician and [name] will be sent to the treating physician's patients notifying them of the study, and informing that an NYULH clinical staff person will contact them to explore their willingness to consider participation, or that their patients can call directly to the study staff to ask about the study. (b) Study staff will call or email patients who agree to be contacted, describe the study and, if the patient expresses an interest, conduct preliminary screening by telephone. Verbal consent is obtained by study staff prior to eligibility screening. (c) For potentially eligible patients with active MyChart accounts that have agreed to be contacted for research and indicate yes under the "recruiting ok?" option on EPIC, study staff will send the already IRB approved email script

via Epic. The patient will receive the message via MyChart and it will automatically be noted on their EHR as an encounter message. (d) Written informed consent will be obtained with subsequent face-to-face visit for eligible participants. An IRB-approved waiver of authorization will be obtained prior to searching the EHR.

Method 2: Participant self-referral through EPIC EHR MyChart alerts: We will provide the NYULH Epic Research Integration team with a list of potentially eligible patients provided to us by NYULH DataCore services through an IRB-approved waiver of authorization. The Epic team will create weekly reports on upcoming appointments from this potentially eligible patient's list, and will send these patients an alert notification two weeks prior to these appointments. These alert will inform patients to check MyChart electronic record for a new message. A modification will be submitted with the alert text prior to starting the study.

We will provide a NYULH Epic Research Integration team with an IRB-approved patient-facing script to be posted in the Epic electronic health record patient portal (MyChart) with a brief study description and encouragement to discuss the study with their treating physician on their next appointment. After this encounter, the Epic Research Integration team will send a second alert to potential participants after their medical appointment for them to check MyChart for another IRB-approved message reminding patients to contact study staff for any questions or to express their interest to participate. At this point, study recruitment proceeds as per protocol: (a) study staff describe the study and, if the patient expresses an interest, conduct preliminary screening by telephone. Verbal consent is obtained by study

staff prior to eligibility screening. (b) Written informed consent will be obtained with subsequent face-to-face visit for eligible participants. A modification will be submitted with the alert text prior to starting the study.

Method 3: Self-referral from advertisements placed in the FHC/FGPs: IRB-approved fliers and brochures containing an overview of the study will be created and displayed in the clinical practice setting for those who may be interested. Interested patients will be provided with the phone number of the study staff that they may call to obtain additional information about the study. Those participants contacting the study office will be provided a brief description of the goals of the study and what their participation would entail. Those who remain interested will be screened to assure that they meet eligibility criteria and schedule an informed consent and eligibility visit. We will contact the patients' healthcare provider/agent to determine if their patient is fit to participate in the study. A modification will be submitted with flyers prior to starting the study.

Method 4: Physician referral: During the provision of routine ambulatory care, physicians will identify potentially eligible participants and ask about their interest in a study that proposes to examine how patient and providers talk about taking medications. Interested patients will be advised to contact the study by telephone to discuss possible enrollment. Interested patients will be provided with the phone number of the investigators that they may call to obtain additional information about the study. Those participants contacting the study office will be provided a brief description of the goals of the study and what their participation

Study Number s18-01044

March 17, 2020 - version 9

would entail. Those who remain interested will be screened to assure that they meet eligibility criteria and schedule an informed consent visit.

Retention Plan

We will use several strategies to retain practices and participants while they are enrolled in the trial. These include: (1) Signed memorandum of understanding (MOU): We have found that this formal agreement ensures that the sites understand the purpose of the study and their roles and responsibilities for participation, which increases the likelihood of retention. The MOU also highlights the benefits of participating in the project. All sites will be asked to sign this agreement as part of the recruitment and enrollment process. (2) Identify a practice champion or key contact to act as a liaison: This is also crucially important to ensure fidelity to the implementation of the MJS DIABETES intervention into the clinic workflow. (3) Offer monetary incentives for participation. For patients, this includes offering appropriate incentives (including cell-phone data plan subsidies), time to complete study visits, periodic phone calls, and transportation to the sites (total incentive: Formative phase: \$60; Clinical Efficacy trial: \$50). PCPs in both phases will be offered an incentive of \$50 for their time. (4) Maintain communication: For patients, following consent, we will request the names, addresses, and telephone numbers of two friends or relatives, so we can contact patients in the event of a missed appointment. This approach has been a helpful strategy in prior trials. We will implement additional strategies that have led to successful retention of racial/ethnic minority patients in clinical trials such as: provision of a toll-free study telephone number; flexible scheduling; and continuity of study staff to maintain a personal connection to the

study. We will also send reminders for upcoming study visits in the form of mailed letters, telephone calls, and secure messages sent through MyChart and doximity. For PCPs, we will maintain contact through an emailed newsletter for these sites that provides updates about national and statewide health care initiatives but does not discuss intervention-related information. We will also remind PCPs of the protocol at the monthly meetings.

To increase enrollment into the study, all participants will also be asked about their ability to receive text messages during the consent procedures. Those individuals who express concern about participating due to the fees associated with receiving text messages (due to either not having a text messaging plan or a limited allowance of messages per month) will receive reimbursement for the messages that are sent as part of the study. Patients who will accrue the most text messaging charges and do not have a text messaging plan will be reimbursed \$25 in total.

6.3.5 On Study Visits

Screening Visit: During this visit, trained RAs will use a standardized form to screen patients based on the study's inclusion and exclusion criteria. Verbal consent will be obtained prior to beginning the eligibility screening. Only patients that meet all eligibility criteria will be scheduled for the face-to-face consent/baseline visit. This visit should take 10 minutes.

Consent/Baseline Visit: At this visit, trained RAs will describe the study in easy-to-understand language. If the patient remains interested, the RA will obtain written informed

Study Number s18-01044

March 17, 2020 - version 9

consent in the patient's preferred language (English or Spanish). Following informed consent, patients will complete the baseline study measures (see Measures Table 7). Finally, patients will be randomized to the intervention or control arms. This visit will take approximately 45 minutes.

Follow-up study visits at 3, 6, and 9-Months (post randomization): Patients will complete self-report measures with a bilingual RA. Patients in the MJS group will also be asked about any challenges to using MJS since their last study visit. The visit will be conducted either via telephone with a RA or REDCap, depending on the patient's preference. These visits will take approximately 30 minutes each.

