For the formative phase, we will use a mixed methods observational design to refine the study intervention.

For the clinical efficacy phase, we will conduct a single-blinded, phase 3 randomized controlled trial.

Study Population

The study population will include primary care providers and patients with uncontrolled type 2 diabetes (T2D) receiving care in the network of Family Health Centers (FHCs) and Faculty Group Practices (FGPs) at NYU Langone Health.

PCP Eligibility Criteria

Inclusion Criteria: (a) Fulltime primary care provider (MD/DO, NP) practicing at the participating FHC and/or FGPs and (b) provides care to at least five patients with a diagnosis of T2D.

Exclusion Criteria: Refuse to participate

Patient Eligibility Criteria

Inclusion Criteria:

- Have a diagnosis of T2D for ≥ 6 months;
- Have uncontrolled T2D defined as HbA1c $> 7\%$ documented in the EHR on at least two visits in the past year;
- Fluency in English or Spanish;
- Be willing to send/receive text messages; and
- Be > 18 years of age.

Exclusion Criteria:

- Refuse or are unable to provide informed consent;
- Have acute renal failure, end stage renal disease (ESRD) or evidence of dialysis, renal transplantation, or other ESRD-related services documented in the electronic health record (EHR);
- Have significant psychiatric comorbidity or reports of substance abuse (as documented in the EHR);
- Are pregnant or planning to become pregnant within 12 months;
- Currently participate in another T2D study; or
- Plan to discontinue care at the clinic within the next 12 months.

Number of Participants

Formative Phase

Patients: 36 patients with uncontrolled T2D

Providers: 14 primary care providers

Clinical Efficacy Trial [Sample includes new participants that did not participate in the formative phase]

Patients: 282 patients with uncontrolled T2D

Study Number s18-01044

March 17, 2020 - version 9

Providers:14 primary care providers

Abbreviations

Abbreviation	Explanation
AHRQ	Agency for Healthcare Research and Quality
DSMP	Data Safety Monitoring Plan
EHR	Electronic Health Record
HbA1c	Hemoglobin A1c
mHealth	Mobile Health
MJS	Modern Journal System
NP	Nurse Practitioner

PCP	Primary Care Provider
PHI	Personal health information
PI	Principal Investigator
PRO	Patient-reported outcome
RCT	Randomized controlled trial
SMBG	Self-monitoring blood glucose
T2D	Type 2 diabetes
TAM3	Technology Acceptance Model-version 3
UC	Usual Care
UCD	User-centered design

Study Number s18-01044

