Low Compliance Message (always triggered if 3 consecutive days are missed): We haven't heard from you in the last 3 days. Text HELP if you need assistance in the journaling program.

Good Compliance Message: You have answered 10 text messages in a row for the

Good Compliance Message: You have answered 12 text messages in a row for the journaling program. Keep it up!

% Completed Message 1: You have responded to 85% of the messages over the past 4 weeks in the journaling program.

% Completed Message 2: Congratulations! You are halfway through the journaling program.

Mobile Opt-in/Opt out Process: After completing informed consent, patients randomized the intervention condition will meet with the RA to receive training on how to use the intervention and opt in to receive SMS messages. Per carrier policies to opt in, patients must provide their mobile numbers and carrier information. Once their information has been added to the system, they will receive a SMS asking them to reply to confirm their participation. To confirm, patients will need to reply via text message.

This step verifies their mobile number and joins them to the intervention. They will receive a welcome message.

To cancel or opt out of the program at any time, patients will be required to send the word 'STOP' to any program message. This information is communicated to the patient at the time of registration, via a Mobile Terms and Conditions document – which they will be required to sign. The opt out information is also communicated to them within the first program confirmation SMS, as well as once a month, in a SMS message sent as part of their subscription service.

Study Number s18-01044

March 17, 2020 - version 9

All additional carrier compliance terms will also be adhered to. A HELP message, and an invalid response message will be developed. Carrier specific rate information will be included in messages as required.

Patients will then be instructed on how to respond to the SMS messages and asked to demonstrate their ability to understand.

Journal report: After the first week, and every 2 weeks thereafter, patients will receive a journal report that visualizes their responses to the text message questions in straightforward graphs and displays the adherence responses in a calendar. The reports are intended to help patients reflect on changes in their responses overtime, and discuss how their symptoms and functioning have changed in between visit.

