6.1.2 Method of Assignment/Randomization

This project has a hierarchical study design with each patient nested within a PCP thus, randomization will occur within PCP. The study statistician ([name]) will oversee randomization, which will be carried out using a SAS macro after completion of the consent procedures and baseline data collection. Patients will be randomly allocated to either the intervention (MJS DIABETES) or UC at a 1:1 ratio. A random number from 0 to 1 will be used to determine to which group the subject is assigned. The standard cut score will be set at 0.5 for the first n subjects from the same PCP. Those who receive a random number between 0 and 0.5 will be assigned to the UC group and those with a random number greater than 0.5 will be assigned to the MJS group. The balance between the groups within each PCP will be carefully weighted after the total number of subjects from a PCP reaches a number greater than n. Before the randomization procedure, the number of subjects randomized to each arm of the study for each PCP will be estimated using SAS macro programs. If more than the n subjects are randomized initially, the cut score for the next subject is equal to the ratio of the experimental arm (n1) to the subjects already randomized

(m) for that PCP (n1/m). The randomization log will be stored in a secure file, and will be password protected. Once a patient has met eligibility criteria and provided consent, the program manager will call the study statistician for the patient's group assignment. As is true for most behavioral interventions, the patient cannot be blinded to the group assignment. However, it is plausible that study staff could bias the study outcome by knowing the patient's group assignment. To mitigate the potential for this bias, the RA that is responsible for data collection will be blinded to the patients' group assignments and study hypotheses (i.e., single blind design).

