6.2.2.1 Adverse Events Definition and Reporting

The Principal Investigator (PI) will be responsible for quality control including reviewing and reporting adverse events. The plan will comprise the following elements:

- Adverse events will be reported to the IRB.
- A detailed plan to address serious events that may arise during study visits, such as HbA1c values that indicate a diabetic emergency, is in place. Critical blood sugar values are defined as: 300 mg/dl or higher OR less than 40 mg/dL). In the event that the RA encounters such readings at any point in the study visit process or via transmission of home readings, the following protocol will be triggered: (1) Let the participant know that these values are very high and recommend follow-up with his/her primary care provider; (2) Alert the study PI and contact the Project Manager to inform that such a reading has occurred; (3) Document all cases on Adverse Event Form. The Project PI and key personnel will meet every 6 months to review adverse events reports, participant complaints, if any, and dropout rates. Data will be provided at those meetings by the investigators on key variables that may indicate harm, including changes in HbA1c and cardiovascular risk profile.
- Any unexpected adverse reactions that are associated with the research and that are fatal or life threatening will be reported to the IRB within 24 hours of discovery. Any unexpected adverse events associated with the study that are moderate to severe in nature, but not life threatening, will be reported to the IRB in 5 days.

Study Number s18-01044

March 17, 2020 - version 9

- Summaries of adverse events reports will be made to AHRQ/Merck in the yearly progress or report or, at the end of year 2, in the final report, unless the nature of a particular event is such that it bears immediate reporting to AHRQ/Merck.
- If a serious adverse event occurs as a result of the study, consideration will be given to stopping the study early. In the event of early stopping of the study, the IRB will be promptly notified.

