6.3.6 End of Study and Follow Up

Final study visit at 12-Months (post randomization): Patients will complete the self-report measures and have their chart review completed. Patients in the MJS group will also complete measures regarding perceived use, ease of use and use behavior. Patients will also complete an exit interview where they will be queried about their experiences using the MJS tool over the past 12 months and recommendations for improvements. The visit will be conducted either via telephone with a RA or REDCap, depending on the patient's preference. This visit will take approximately one hour.

In addition, providers will be asked to complete measures regarding perceived use, ease of use, use behavior and physician communication at 12 months. Providers will also complete an exit interview where they will be queried about their experiences using the MJS-EHR interface over the past 12 months and recommendations for improvements. The ECR tool

interface over the past 12 months and recommendations for improvements. The PCP study visit will take approximately 30 minutes.

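### The outcome-collecting RA is declared blinded, but telephone visits that collect the self-report outcomes also carry MJS-only questions assigned to nobody else

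*Combined protocol and SAP*

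**What the plan says.** The Synopsis (Study Design) states that "we will conduct a single-blinded, phase 3 randomized controlled trial". Section 6.1.2 accepts that patients will know their arm and explains why staff should not: "it is plausible that study staff could bias the study outcome by knowing the patient's group assignment". The safeguard is that "the RA that is responsible for data collection will be blinded" to both assignment and hypotheses, and the section equates this with the single-blind design.

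The visit and data sections then say:

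- **6.3.5 (months 3, 6, 9):** a bilingual RA takes patients through the self-report measures, by telephone or in REDCap as the patient prefers. At these visits, "Patients in the MJS group will also be asked about any challenges to using MJS since their last study visit".
- **6.3.6 (month 12):** the mode choice is the same. After the self-report measures, "Patients in the MJS group will also complete measures regarding perceived use, ease of use and use behavior", and there is an exit interview about using the tool.
- **7.5:** the exit interview is held by telephone with the RA or completed in REDCap.
- **7.5.1:** a trained RA obtains every measure. Process measures are the one class that differs between arms.
- **6.1.1 (opt-in process):** "patients randomized the intervention condition will meet with the RA to receive training".
- **6.3.4 (Retention Plan):** patients are to keep dealing with the same study staff, as a retention strategy.

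**The concern.** RA blinding is the only masking this trial claims, and 6.1.2 introduces it to prevent a bias the plan itself regards as plausible. If the person collecting outcomes by telephone must also handle questions that exist only for one arm, the procedures undo the safeguard.

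The outcomes at stake are the self-report ones: the self-care behaviours behind Hypothesis 2a, and the four mediators in 5.2.2 (knowledge, self-efficacy, outcome expectations, patient-provider communication) behind Hypothesis 2b. An interviewer who knows the arm may probe, prompt or record answers differently. The trial could then report blinded assessment of these outcomes without having had it.

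**Working it through.** The documents give no figure that bears on this point, so the check sets the sections side by side.

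1. **What the blinding claim covers.** Under 6.1.2 it covers the RA responsible for data collection. Patients are excluded from it, and 6.1.2 has the program manager obtain each assignment from the statistician. If the RA is unblinded, nothing remains of the single-blind label.

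2. **Who handles the MJS-only items.** Section 6.3.5 uses the passive voice and does not name who asks. However, the visit has only two modes, RA by telephone or REDCap, and no other role appears in it. Section 7.5 names the RA for the telephone exit interview, and 7.5.1 has an RA obtain all measures, process measures included. For a telephone visit, the natural reading is that the RA asks.

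3. **How the telephone RA learns the arm.** There are three possibilities. The RA is told beforehand whom to ask; the form opens the item only for MJS patients; or the RA asks everyone and hears the answer. Each reveals the arm. It also works in reverse: a patient for whom the item does not apply is in usual care.

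4. **When that knowledge can reach the outcomes.** There are four post-baseline collections: months 3, 6, 9 and 12. Take a patient who uses the telephone throughout with the same RA.
   - If the RA knows the arm before or during the outcome measures, all 4 collections are exposed.
   - If the MJS items always come last and the RA has no advance list, month 3 is protected and 4 − 1 = 3 remain exposed (months 6, 9 and 12).
   - Month 12, the time point of Hypotheses 2a and 2b, is exposed either way, because three visits with MJS questions precede it. The staff continuity promised in 6.3.4 makes this carry-over likely.

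5. **What lies outside the problem.** Baseline measures precede randomisation (6.1.2, 6.3.5). A visit completed in REDCap need not involve an interviewer. HbA1c comes from the health record (5.2.1, 6.2.1).

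6. **Whether any provision separates the roles.** None was found. No section gives the MJS items to an unblinded person, fixes their order as a rule, locks the outcomes first or provides a separate form. The safeguards in Table 6 concern usual-care patients gaining access to MJS and PCPs opening the wrong interface. They do not address what the outcome assessor knows.

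**The case against.** The strongest reply is that the breach is inferred. Section 6.3.5 does not say who asks, the protocol refers to several RAs, and 6.1.2 blinds only the one who collects data. It is true that a different RA could train MJS patients. A reader might infer from 6.1.1 that the outcome RA is unblinded at training; the documents do not support that, because they never say the trainer and the assessor are the same person. The point about months 3, 6 and 9 does not need that step. There the MJS questions sit inside the outcome visit itself.

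Second, patients may choose REDCap. This stands, and it confines the problem to telephone visits. It does not remove it, because the mode is the patient's choice and the telephone share is unknown.

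Third, 6.3.6 lists the self-report measures before the MJS items, and month 12 is the last visit. This also stands: the month 12 items add little by themselves. What matters at month 12 is knowledge carried over from earlier visits.

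Two further inferences are tempting and unsupported. One is that the glucose alert in 6.2.2.1, which covers values met at visits "or via transmission of home readings", reveals the arm. That section names no arm, and 5.1 limits self-monitored glucose reporting to insulin-dependent MJS patients, so it cannot show that RAs learn assignments in general. The other is that the false-positive rate on the self-report outcomes can be calculated. That needs an interviewer effect the documents do not give, and any such effect could not be separated from the bias of patients who know their arm.

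**Conclusion.** Wrong as written, within limits. The plan claims a blinded outcome collector, yet its visit procedures place arm-revealing questions in the telephone visits that collect the self-report secondary outcomes and mediators, with nobody else assigned to them. For a patient seen by telephone by one RA throughout, three or four of the four post-baseline collections are exposed, month 12 among them.

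This rests on two assumptions: that the RA conducting a telephone visit asks the MJS items, which is the natural reading of 6.3.5, 7.5 and 7.5.1 together, and that the same RA sees the patient again, which 6.3.4 encourages. The direction and size of any bias are unknown.

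A reader might go further and conclude that the trial has no blinding at all or that the primary result is compromised. The documents do not support either. REDCap visits and baseline measures stay outside the problem, and HbA1c from the health record is little exposed to interviewer bias.

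**What to change.** In 6.3.5 and 6.3.6:

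- Collect the MJS-challenge questions, MJS process measures and exit interview only through a separate REDCap form, or through a staff member who is already unblinded. They should never go through the RA who collects outcomes.
- Open these items only after that visit's outcome measures are completed and locked. Locking alone is not enough: if the same RA then asks the MJS items, that visit is protected but later ones are not.

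In 6.1.1 or 6.1.2, state that the RA who trains an MJS patient does not collect outcomes from that patient.

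If this cannot be arranged, withdraw the RA-blinded claim for telephone-collected self-report outcomes and describe their assessment as unblinded.

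The cost is a form split and some allocation of tasks among existing staff. REDCap is already in use and the plan already refers to several RAs. Training can stay with an RA. Moving it to the program manager would mean about 141 one-to-one in-person sessions (141 per group in 6.4.2; training format in Table 6), and this point does not require it. If a person rather than a form asks the MJS items, that person must be able to work in Spanish; the plan does not say whether the program manager can.
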